Children between 10-17 years of age presenting to the UIHC and Blank Children's Hospital with an unintentional injury requiring admission will be the sample population. Blank Children's Hospital has submitted a separate IRB for their participation in the study. A child will be included if they are 10-17 years old with an unintentional injury. Consenting children and their parents will be asked to complete a series of four questionnaires: before hospital discharge, at 6 weeks post discharge, 3-months and 6-months post discharge. The parent-child dyads will be randomized (1:1) to receive training in Link for Injured Kids or to receive Trauma Education (parent booklet, "So, you've been in an Accident"). The survey completed in the hospital will be a paper survey or online via iPads, and follow-up surveys can be completed on paper or online.

1.5 *Specify your research question(s), study aims or hypotheses (do not indicate "see protocol")*

Phase 1

Assess the feasibility of LPC for Injured Kids through qualitative research with parents of previously injured children and social workers and pediatric trauma providers from the UI Children's Hospital and Blank Children's Hospital. The focus group findings will also help inform and refine intervention materials and delivery.

Phase 2

Through a randomized trial, determine the range of potential psychosocial and behavioral health indicators possibly impacted by Link for Injured Kids. This will identify the types of outcomes which could include PTSD, depression, nonspecific distress, quality of life, absenteeism, school performance, coping skills, communication skills, and access to mental health.

1.6 *Background and significance and/or Preliminary studies related to this project. (do not indicate "see protocol")*

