Provider population: Emergency Medicine and Trauma physicians, nurses, pediatric psychiatrists and psychologists, social workers, child life specialist and parent advocates serving the pediatric unintentional traumatic injury population.

Phase 2

Children with new unintentional injuries (not a complication from previous injury) will be recruited to participate in the randomized trial. All children will be between the ages of 10-17.2 (17 years, 3 months) years of age. All children admitted for injury will be identified, and direct questioning later will screen out those who had intentional injuries. Children with unintentional injuries will be administered the COAT which is a measure of orientation to self, place and memory, and those that pass the COAT will be recruited into the study. One parent of the child will be recruited for participation. Inclusion and exclusion criteria are the same for both randomization groups. Exclusions include non-English speaking, diagnosis of intellectual deficit or psychosis, suicide attempt in the last year, and residential treatment placement in the last year.

VI.14 *Provide an estimate of the total number of subjects that would be eligible for inclusion in each of your study populations (include your control population if applicable)*

Phase 1

University of Iowa Children's Hospital-UI Children's(complete)

Parent population- UI Children's: Approximately 140 pediatric patients between the age of 10 and 18 are treated by UI Children's Hospital each year, therefore, approximately 140 parents will be eligible for participation in the focus group.

Provider population- UI Children's: Approximately 10-15 UI Children's Hospital providers serve the injured pediatric population. All providers will be eligible for the focus group or a personal interview.

Blank Children's Hospital- Complete

Parent Population-Approximately 100 pediatric patients between the age of 10 and 18 are treated by Blank Children's Hospital each year, therefore, approximately 100 parents will be eligible for participation in the focus group.

Provider population- Approximately 10-15 Blank Children's Hospital providers serve the injured pediatric population. All providers will be eligible for the focus group or a personal interview.

Phase 2

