- Other - Phase 1 - Blank Children's Hospital will use Name, address and telephone contact information for parents of children identified in the Blank Children's Trauma system as having an unintentional injury. Blank Children's Hospital staff will do mailing of introductory letter so no PHI will be shared with UI research staff.

VII.D.2 List the individual data elements you will need to access/use from the patient or clinic records to identify potential subjects for recruitment

Phase 1

- Injured child's age to ensure the child is between 10 and 17 years of age
- Type of injury to determine intention
- Parent names
- Parent address to send informational sheet and consent letter
- Parent phone numbers to follow-up after study information sheet

Phase 2

- Injured child's age to ensure the child is between 10 and 17.2 years of age
- Admission to UIHC and Children's Mercy Hospital Pediatric Unit for injury. Later, direct questioning will be used to determine whether the injury was intentional, and thus if the child is eligible.
- Parent and child names

VII.D.3 Describe why you could not practicably recruit subjects without access to and use of the information described above

Phase 1

Unintentional injuries among children ages 10-17 are not rare but severe injury requiring a visit to an Emergency Department and Trauma activation are difficult to identify. Use of the Iowa Trauma database allows the researchers to identify this high risk population.

Phase 2

Unintentional injuries among children ages 10-17 are not rare but severe requiring a visit to an Emergency Department, Trauma activation and hospital admission. These are difficult to identify. Use of medical record data allows the researchers to identify this high risk population.

- VII.D.4** *Describe why you could not practicably obtain authorization from potential subjects to review their patient or clinic records for recruitment purposes.*
It would not be practicable to contact subjects to ask if you can review the medical record to see if they are eligible because you won't know who to contact until you do review the medical record.
- VII.D.5** *Describe plans to protect the identifiers from improper use or disclosure*
All identifying information will be kept in password-protected computer files that are only available to the research team.
- VII.D.6** *Describe plans to destroy identifiers at the earliest opportunity consistent with conduct of the research*
Phase 1

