- *Describe the steps that will be taken by the research team to minimize the possibility of coercion or undue influence during the consent process*

The ICTS flexible nursing staff will alert the research team if a child presents to the UIHC as an admission for trauma. Children's Mercy Hospital research staff will be alerted by Emergency Room staff if a child present for admission of a trauma. The research team will review the child's medical record to determine if he/she meet eligibility criteria, and consult the child's care team to verify that the injury was indeed unintentional. On a daily basis, the research team will review each child's medical record to determine when the child is likely to be discharged. On the day of discharge, a member of the research team will present to the child's room to determine if the child has an appropriate level of consciousness to complete the consent process, and if appropriate recruit the dyad. If timing is inconvenient due to a conflicting event, such as a medical procedure, the team member will give the PCORI infographic to the parent. This half-sheet contains brief information about the study and contact information for the study team. The team member will only give this half-sheet to families they have approached in

person, and they will return at a more convenient time to continue the recruitment process. The child-parent dyad will be recruited simultaneously therefore the parent or legal guardian will be available at the time of the child's assent. The team member will discuss the study and complete the consent process with the dyad in-person. To minimize the possibility of coercion during the consent process, the research team will follow the consent document closely and stress to the dyad that the child's health care will not be affected by participation in the study.

For research subjects that were assented as children but turned 18 prior to the end of their involvement in the study, the research team will mail a re-consent instruction letter along with a new consent document to the subject. The consent document will be different than the consent document signed by the parent at initial recruitment. The documents will be mailed to research subjects via U.S. mail and provided a postage paid envelope in which to return the signed consent document to the research team.

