VII.D.31 *What are the plans for the assent process for children/minors in this study? (You may choose more than one procedure if you have different child populations in your study)*

- Children/minors will sign an assent or consent document -

VII.D.36 *Provide a detailed description and rationale for each of the procedures chosen above and describe the child/minor populations to which they apply in your study.*

Phase 2

All children 10-17.2 years of age will be asked to sign an assent document. We chose to use the assent document for all participants aged 10-17.2 years because the language is simple and easy to understand, especially since the children are undergoing medical procedures in the hospital.

It was discovered on 7/15/2016 that some children who signed the assent document turned 18 at some point during the 9-month follow-up period of the study. For research subjects that were assented as children but turned 18 prior to the end of their involvement in the study, the research team will mail a re-consent instruction letter along with a new consent document to the subject. The consent document will be different than the consent document signed by the parent at initial recruitment. The documents will be mailed to research subjects via U.S. mail and provided a postage paid envelope in which to return the signed consent document to the research team.

VII.D.37 *Does the study include any form of deception (e.g., providing participants with false information, misleading information, or withholding information about certain study procedures)?*

Examples:

- *Procedure includes a cover story that provides a plausible but inaccurate account of the purposes of the research.*
- *Participants will be provided with false information regarding the particular behaviors of interest in the research.*
- *Procedures include a confederate pretending to be another participant in the study.*
- *Participants will be told that the research includes completion of a particular task, when in fact, that task will not be administered.*
- *Study is designed to introduce a new procedure (or task) that participants are not initially told about.*
- *If yes, a waiver of informed consent must be requested under question IV.3.*

No

VII.E. Project Description (E)

VII.E.1 *Will subjects be randomized?*

Yes

VII.E.1.a *Will any subjects be blinded to which study arm they have been assigned?*

No

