Link Intervention: Intervention parents will get a 20-45 minute training on the Link for Injured Kids Program during their child's hospitalization. The training will involve viewing a Link training program on an iPad and a brief training in motivational interviewing. All Link training sessions will be audio recorded to ensure fidelity among the research team. Two weeks after hospital discharge, a packet will be

mailed to the family's home address containing the Link pocket card, trifold, and instructional DVD. At 6-weeks post-discharge, the instructor will conduct a telephone booster session with the parent trained in Link.

Trauma Education Intervention: Parents will be given the booklet "So Your Child Has Been in an Accident... An Information Booklet for Parents." This booklet will be sent again to the family's address 2-weeks after their hospital release. At 6-weeks post-discharge, the interventionist will conduct a brief telephone survey to assess the parent's perceptions regarding the Trauma Education program.

All subjects: The dyads will be asked to complete follow-up questionnaires at 6 weeks, 3-months, 6-months post hospitalization. The questionnaire will measure depressive symptoms, symptoms of post traumatic stress disorder, social support, family communication, strengths and difficulties and quality of life and asks about any mental health or community resources they may have used since the last questionnaire. The research team will e-mail a link for the parent and the child to complete their surveys as well as mail a hard copy version of the questionnaire with a cover letter explaining that the survey can be completed on paper or online and a postage paid envelope. If completed online, the questionnaires will be done electronically using REDCap, a U of I supported online survey system. A telephone call will be placed to the dyad the day the hard copy questionnaire is mailed informing the dyad of the mailing; the dyad will also have the option of completing the survey over the phone at the time of the call.

For subjects that were consented as children, but turned 18 prior to the end of their involvement in the study: after obtaining re-consent when the subject turns 18, these subjects will complete follow up questionnaires at the same intervals described for all subjects.

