If an online or mailed questionnaire is not returned within 7 days the research team will attempt to contact the dyad by phone 12 times (for each follow-up period) to remind them to complete the questionnaire or to make arrangements for the questionnaire to be completed at an already scheduled follow-up appointment at the hospital. For 6-week questionnaire, they will be contacted 12 times up to 6 weeks following their eligibility to complete that questionnaire. For 3-month questionnaire, they will be contacted 12 times up to 3 months following their eligibility to complete that questionnaire. For 6-month questionnaire they will be contacted 12 times up to 6 months following their eligibility to complete that questionnaire. After a month of no response for any survey timepoint, we will resend the package or online link. If a dyad does not complete the 6-week questionnaire, they will still be asked to complete the 3-month and 6-month questionnaires.

The research team will complete the medical record abstraction within 12 months of receiving the medical record consent. The data collected from the medical record includes measures of injury severity, the type of injury the child sustained, external cause of injury, length of stay, diagnostic procedures, Glasgow Coma Scale measures, comorbidities, and initial vital signs and all discharge codes.

VII.E.7 *Will you attempt to recontact subjects who are lost to follow-up?*

No - those lost to followup will not be recontacted

VII.E.9 *Will subjects be provided any compensation for participating in this study?*

Yes

VII.E.10 *Cash*

No

VII.E.11 *Gift Card*

No

VII.E.12 *Check*

Yes

VII.E.13 *Who will be providing the research compensation check to the subject?*

Accounting Services directly via the e-Voucher system

VII.E.16 *Other*

Yes

VII.E.17 *Describe:*

Phase 1: A light meal will be provided to all focus groups. For the parent focus groups, on-site child care will also be provided.

Phase 2: None

VII.E.18 *If you plan to compensate subjects using cash, checks or cash equivalent does your unit have a [Cash Handling Procedure](#) in place that has been approved by Accounting Services?*

Yes

VII.E.19 *Describe the compensation plan including*

- *Compensation amount and type per visit*
- *Total compensation*
- *Pro-rating for early withdrawal from study*

Phase 1

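### Do the differing follow-up lengths (6, 9 or 12 months) and age limits (17.2 or 17) leave it open who must re-consent at 18?

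*Protocol*

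**What the plan says.** **Length of follow-up.** Protocol VII.E.6 gives the schedule: "The dyads will be asked to complete follow-up questionnaires at 6 weeks, 3-months, 6-months post hospitalization". Sections 1.4 and VII.E.4 give the same time points. VII.E.6 also limits reminders for the last form: "For 6-month questionnaire they will be contacted 12 times up to 6 months following their eligibility to complete that questionnaire". VII.D.36, reporting a discovery dated 7/15/2016, says that "some children who signed the assent document turned 18 at some point during the 9-month follow-up period of the study".

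**Age limit in Phase 2.** VI.13, where the form asks for inclusion and exclusion criteria, says: "All children will be between the ages of 10-17.2 (17 years, 3 months) years of age". VI.8 and VII.D.36 also give 17.2, and VII.D.2 has staff "ensure the child is between 10 and 17.2 years of age". The lay summary in 1.4 says: "A child will be included if they are 10-17 years old with an unintentional injury". VI.15 (finding candidates in admission records) and the Phase 2 rationale in VII.D.3 also use 10-17.

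**Re-consent.** VII.D.29, VII.D.30 and VII.D.36 share one rule: for subjects who assented as children but "turned 18 prior to the end of their involvement in the study, the research team will mail a re-consent instruction letter" with a new consent document. VII.E.6 adds that "after obtaining re-consent when the subject turns 18, these subjects will complete follow up questionnaires at the same intervals described for all subjects".

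**The concern.** The re-consent rule depends on the end of a subject's involvement, and no section gives that end as a month. Three values can be read from the text: 6 months (last scheduled form), 9 months (VII.D.36) and 12 months (last permitted reminder). The age cap interacts with them, because a child entering at 17 years 3 months reaches 18 exactly 9 months later. The cap therefore keeps children under 18 if involvement ends by month 9, but not if a form is still being requested in months 9 to 12. If 10-17 were read as running up to the 18th birthday, a child entering after 17 years 6 months would be 18 before the 6-month form fell due.

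Two things would be at stake: valid consent for data taken from a subject who is now an adult, and completeness of the child-reported 6-month data, since re-consent means a mailed document that must be signed and returned. The protocol records that children did turn 18 during follow-up, so the worry is not fanciful.

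**Working it through.** **Inputs.** Last form at 6 months (1.4, VII.E.4, VII.E.6); reminder limit of 6 further months (VII.E.6); follow-up of 9 months (VII.D.36); lower age 10 years = 120 months; cap 17 years 3 months = 207 months (VI.13); 18 years = 216 months; 300 minors (VI.6, XI.2).

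**Step 1: can the 9 months be reproduced?** Reminder windows close at 1.5 + 1.5 = 3 months for the 6-week form, 3 + 3 = 6 for the 3-month form and 6 + 6 = 12 for the 6-month form. The schedule ends at 6. Nothing in the schedule or windows gives 9. The only match is 216 - 207 = 9, the time from the cap to the 18th birthday. The protocol does not say that the cap was set this way.

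**Step 2: age of the oldest eligible child.**

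| Time point | Age in months | Age |
|---|---|---|
| Month 6 | 207 + 6 = 213 | 17y9m |
| Month 9 | 207 + 9 = 216 | 18y0m |
| Month 12 | 207 + 12 = 219 | 18y3m |

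Under the cap nobody is 18 when the last form falls due, and nobody turns 18 before month 9. Reading 17.2 as a decimal gives 17.2 x 12 = 206.4 months, or 216 - 206.4 = 9.6 months to the 18th birthday, which is slightly more room.

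**Step 3: how many children turn 18 before each candidate end?** Assumption: 300 children with ages spread evenly. This is illustrative, as the protocol gives no age distribution.

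| End | Cap at 17y3m (range 207 - 120 = 87 months) | 10-17 read as up to 18 (range 216 - 120 = 96 months) |
|---|---|---|
| Month 6 | 0 | 300 x 6/96 = 18.8 |
| Month 9 | 0 | 300 x 9/96 = 28.1 |
| Month 12 | 300 x 3/87 = 10.3 | 300 x 12/96 = 37.5 |

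The 10.3 becomes 5.2 or 20.7 if the oldest ages are half or twice as common as average. It counts everyone who turns 18 in months 9 to 12. Re-consent matters only for those whose 6-month form is still outstanding, at least three months after it fell due. The protocol gives no rate for this. If 10% to 20% were outstanding (an assumption), 10.3 x 0.1 = 1.0 to 10.3 x 0.2 = 2.1 children of 300 would be affected.

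**Step 4: what does the re-consent rule need?** It needs a birthday and knowledge of whether a form is still to be requested. VII.E.6 ties re-consent to the time the subject turns 18 and has it precede further questionnaires. A subject who turns 18 with a form outstanding is covered whether the form comes back in month 7 or month 11. The 9-month figure does not enter the rule.

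**Step 5: which age limit governs?** VI.13 is the section that sets the criteria, and it spells out the cap. Section 1.4 is a lay summary. VI.15 uses 10-17 to find candidates and then has the team check inclusion criteria. A child of 17 years 2 months is also 17 years old, so 10-17 can be read as coarser wording of the same range. The right-hand column of Step 3 arises only if staff disregard a limit stated in VI.8, VI.13, VII.D.2 and VII.D.36.

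**The case for a change.** The strongest case for acting is that consent should not depend on a reader's inference. A site that takes month 6 or 9 as the end could conclude that no capped child ever needs re-consent, yet still be chasing a 6-month form from someone who turned 18 in month 10. Both practices can point to the text. The protocol also says that the earlier cases were discovered, which suggests that nobody was watching for birthdays, and the re-consent sections describe no advance flag. These matters belong in the protocol and cannot be left to an analysis plan.

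Part of this stands. The 9-month figure disagrees with the schedule, the age limit is worded in two ways, and 17.2 as a decimal is 17 years 2.4 months rather than 17 years 3 months.

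The rest does not carry. A limit on reminders is not a second end of follow-up, and a subject still being asked for a form is plainly still involved, so the rule reaches that person. The earlier cases do not show that the present text fails: a child within the cap cannot turn 18 before month 9, so those found to have done so within a 9-month period probably entered above the present cap. That is an inference, since the protocol does not give their entry ages. Tracking birthdays is something staff must already do to apply the rule as written.

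**Conclusion.** The concern rests on genuine but clerical inconsistencies, and no change to the plan follows. Applied as written, with the cap in VI.13 and re-consent on turning 18, the protocol leaves no subject with an outstanding form outside the re-consent rule. Under the cap the number turning 18 by month 6 or before month 9 is zero. About 10 of 300 (5 to 21 under the range shown) would turn 18 in months 9 to 12, and perhaps 1 or 2 of them would still have a form outstanding. Those counts assume evenly spread ages and a 10% to 20% late rate, neither of which comes from the protocol. The larger figures of about 19, 28 and 38 require the stated cap to be disregarded.

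The same rules apply in both arms and parent forms are unaffected, so there is no route to bias between arms. Sample size, outcomes and tests do not depend on the point. Tidier wording would be welcome whenever the document is next revised, but no result or conclusion would change.
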